#### 6.4 STUDY INTERVENTION COMPLIANCE

Participants who are inadvertently enrolled, despite significant deviation from protocol-specified inclusion/exclusion criteria, will be discontinued from participation in the study. Participants will be scheduled for follow-up visits and followed for 8 weeks post-treatment for safety per protocol.

At each post-baseline visit, participants will be questioned as to concomitant medications, as well as exclusionary criteria to ensure protocol compliance. Urine drug screens will be performed during the screening visit (Day -14 to Day -2), at the Days 7 (if conducted in-clinic), 28, and 84 visits for all participants. Dosing compliance will be assessed when the participant returns the study drug (both bottles) to the investigator, at which time the study drug bottles will be weighed.

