## 7 STUDY INTERVENTION DISCONTINUATION AND PARTICIPANT DISCONTINUATION/WITHDRAWAL

### 7.1 DISCONTINUATION OF STUDY INTERVENTION

The investigator may discontinue the study drug at any time if there is a safety concern. If the study drug is discontinued, then the participant will early exit from the study. If the participant has discontinued the study drug because of an SAE related to the study drug, that participant should be monitored for at least 30 days or until the SAE has resolved or stabilized.

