#### 8.3.11 EVENTS OF SPECIAL INTEREST

Based on the observed reversible liver enzyme increases in animal models and humans in a clinical setting using the oral formulation nintedanib, abnormal liver function test results meeting the criteria below will be monitored and may trigger a meeting of the Independent Data Monitoring Committee (IDMC):

- ALT or AST >8x ULN
- ALT or AST >5x ULN for more than 2 weeks
- ALT or AST >3x ULN and (total bilirubin >2x ULN or International Normalized Ratio [INR] >1.5)
- ALT or AST >3x ULN with the appearance of worsening of fatigue, nausea, vomiting, right upper quadrant pain or tenderness, fever, rash, or eosinophilia
- Any other safety signals observed during routine data review that warrant convening of the IDMC, in the opinion of the Medical Monitor

Any of these parameters also represent a trigger for interruption of dose for the participant until the IDMC has been convened and a recommendation provided.

In the event of an increase in serum AST or ALT to >3x ULN, the following monitoring will be required:

- Repeat testing within 48 to 72 hours of ALT, AST, ALP, and total bilirubin to confirm the abnormalities and to determine if they are increasing or decreasing
- Participants will be questioned on the presence of symptoms (eg appearance of worsening of fatigue, nausea, vomiting, right upper quadrant pain or tenderness, fever, rash, or eosinophilia)

- If symptoms persist or repeat testing shows ALT/AST >3x ULN for the participants with normal baseline measures or 2-fold increases above baseline values for participants with elevated values before drug exposure, the following measures will be initiated to determine whether the abnormalities are improving or worsening:
  - Interrupt study treatment dosing until advice from the Medical Monitor is provided
  - Repeat liver tests (ALT, AST, ALP, and total bilirubin) 2 or 3 times weekly. Frequency of testing can decrease to once a week or less if abnormalities stabilize or study drug has been discontinued and participant is asymptomatic
  - Obtain a more detailed history of symptoms and prior or concurrent diseases
  - Obtain a history of concomitant drug use (including nonprescription medications, herbal and dietary supplement preparations), alcohol use, recreational drug use, and special diets
  - Obtain a history of exposure to environmental chemical agents
  - Obtain additional tests to evaluate liver function, as appropriate (e.g., INR)

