### 9.3 POPULATIONS FOR ANALYSES

Three analysis populations will be defined and used in the statistical analyses: (1) a safety population, (2) a modified intent-to-treat (mITT) population, and (3) a per-protocol (PP) population.

Safety analyses will evaluate all randomized participants who received at least 1 dose of study drug and attended a post-baseline visit. Results will be presented based on the treatment received.

The primary statistical analyses will evaluate the mITT population, defined as all randomized participants who received at least 1 dose of study drug and had conjunctival hyperemia evaluated at both the Day 1 and Day 28 visits. Results will be presented based on the treatment assigned during randomization.

As a sensitivity analysis, the primary efficacy endpoint of conjunctival hyperemia will also be evaluated in the PP population of participants, who had no major protocol violations. Nominal data will be analyzed using the Pearson chi-square test or Fisher exact test. Conjunctival hyperemia, pterygium vascularity, BCVA, ophthalmoscopy, AS-OCT, and IOP data will be analyzed using analysis of variance models with dose strength as main effects. The analysis will be based on observed data. Missing values will not be imputed.

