5.3 Modified Intent-to-Treat Population

The modified intent-to-treat (mITT) population will include all randomized participants who receive at least one dose of study eye drop and had conjunctival hyperemia evaluated at both the Day 1 and Day 28 visits. This is the efficacy population. Results will be presented by the treatment assigned during randomization.

The primary efficacy analyses will be conducted using the mITT population.

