6 STATISTICAL METHODS

All data processing, summarization, and analyses will be performed using SAS® Version 9.4 or higher.

Unless otherwise specified, for continuous variables, descriptive statistics will include the number of participants/eyes (n), mean, standard deviation, median, minimum and maximum values. Categorical variables will be summarized using frequency and percentages.

Unless, otherwise stated, missing data will be handled as is, except when the aforementioned dates are required for calculations, the partial dates will have either '01' or 'Jan' imputed with an exception for dates related to AEs where the date closest to the last event (screening, first dose, last dose, etc.) should be used rather than arbitrary '01' of that month.

All efficacy data will be summarized by treatment group and time point using appropriate descriptive statistics. Summaries will be presented for both the mITT and PP populations. Due to the small number of participants that are expected to be enrolled at each center, all summaries and analyses will be performed using data pooled across centers.

Baseline results will be those recorded prior to dosing. In cases where more than one pre-dose observation has been recorded, the **last recording** will be identified as the baseline result.

Study days will be numbered relative to the date of the first dosing. The start of study (Day 1) will be defined as the date on which a participant takes the first dose of any study medication, as recorded on the CRF. Relative to study start, days will be numbered ...-2, -1, 1, 2, ... with Day - 1 being the day prior to the start of study medication (Pre-Dose).

Recorded data will be assigned to evaluation/assessment windows. If more than one clinical evaluation is made within a window for a particular visit, the record with the date closest to the targeted window will be used except for AEs where the **worst assessment** will be used.

Visit windows and analytical windows are defined as follow:

Visit	Targeted Window	Analytical Window
Pre-dose (Screening)	Day -14 to Day -1	Day -18 to Day -1
Visit 1 (First dosing date)	Day 1	Day 1
Visit 2 (optional)	Day 7 (± 3 day)	Day 2 to Day 16
Visit 3 (End of treatment visit)	Day 28 (± 3 days)	Day 17 to 3 days after the last dose and up to Day 42
Visit 4	Day 56 (± 5 days)	Day 43 to Day 70
Visit 5 (End of study visit)	Day 84 (± 5 days)	Day 71 to End of Study

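### Read as a cap, the Visit 3 window leaves a Day 28 photograph taken while dosing is still on hold in no visit, so an observed primary score can go unused

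*SAP*

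**What the plan says.** SAP 6 states that "Recorded data will be assigned to evaluation/assessment windows". Visit 3 is scheduled for Day 28 ±3 days and has the analytical window "Day 17 to 3 days after the last dose and up to Day 42". The Visit 4 window is "Day 43 to Day 70". No rule covers a record that falls between them.

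SAP 5.3 admits to mITT, the primary efficacy set, participants who were randomized, took at least one dose and "had conjunctival hyperemia evaluated at both the Day 1 and Day 28 visits". It does not mention dosing status at Day 28. Protocol 9.3 adds "Missing values will not be imputed".

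Four provisions decide who can attend Day 28 without a recent dose:

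- Protocol 8.3.11 foresees an open-ended hold without exit. For confirmed liver enzyme rises the instruction is "Interrupt study treatment dosing until advice from the Medical Monitor is provided", and safety triggers for the monitoring committee also interrupt dosing. SAP 3.7 records interruption separately from withdrawal for any adverse event.
- Protocol 6.4, on participants enrolled in error and then discontinued, says "Participants will be scheduled for follow-up visits and followed for 8 weeks post-treatment for safety per protocol".
- Protocol 7.1 says "If the study drug is discontinued, then the participant will early exit from the study". SAP 6.2.3 maps efficacy data from such an exit to the next scheduled visit and counts them as observed.
- The notes to the schedule in Protocol 1.3 place the Day 28 morning dose in the clinic, before every procedure except the questionnaire.

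**The concern.** The window ties the primary time point to each participant's own last dose. Someone still on hold can attend Day 28 on schedule and be photographed and graded, yet the record matches no row of the window table. The model in SAP Appendix 2 regresses the change score on treatment. Without a Day 28 value there is no change score, and nothing is imputed. The participant may meet the mITT wording and still contribute nothing.

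Being off drug at Day 28 arises after randomization and may depend on arm. Using it to decide whether an observed score counts puts an on-drug condition into the primary analysis that SAP 5.3 does not state.

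It also sits badly with SAP 6.2.3. An exit score from, say, Day 10 after stopping drug is carried to Day 28 as observed data, while a photograph actually taken on Day 28 during a hold is not placed anywhere.

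**Working it through.** **Inputs.** L is the study day of the last dose and V the study day of the visit. Visit 3 opens on Day 17 and, on the cap reading, closes at the earlier of L + 3 and Day 42; Visit 4 opens on Day 43 (SAP 6). The scheduled visit falls on Days 25 to 31 (Protocol 1.3). Planning values are 20 per arm, SD 1.0 and a difference of 1 (Protocol 9.2).

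**1. When a Day 28 visit counts.** The condition is 17 ≤ V ≤ min(L + 3, 42). For V from 25 to 31 this reduces to L ≥ V − 3.

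- V = 25: last dose on Day 22 or later; unassigned if Day 21 or earlier.
- V = 28: last dose on Day 25 or later; unassigned if Day 24 or earlier.
- V = 31: last dose on Day 28 or later; unassigned if Day 27 or earlier.

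**2. Extent of the gap.** Unassigned days run from L + 4 (or Day 17, if later) to Day 42. With L = 20 the window is Days 17 to 23, and Days 24 to 42 belong to no visit. With L = 13 the window would close on Day 16, before it opens, so it is empty; the same holds for any earlier last dose.

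**3. Who is not affected.** Anyone on drug, or back on it by the visit, is dosed in clinic first, so L = V. Then V ≤ L + 3 always holds, and every visit from Day 17 to Day 42 is assigned.

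**4. The proposed window.** Days 17 to 42 regardless of L contain every visit day from 25 to 31. The gap is zero.

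**5. Overlap with the per-protocol set.** SAP 5.4 requires 4 of the 6 doses just before the visit. At three doses a day, six doses span two days. Affected participants have L ≤ V − 4, so they took 0 of those 6 and already fail the rule.

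**6. Size.** The plan gives no figure for this problem; its power statement is useful only for scale. With means (0, 0, 1), the sum of squared deviations from the overall mean is 1/9 + 1/9 + 4/9 = 2/3, so the noncentrality is 20 × 2/3 = 13.33. A one-way ANOVA with 3 × 20 participants at α = 0.05 then has power 0.8997, which matches the stated 90% after rounding. Losing one participant from the arm that differs gives 0.889; losing two gives 0.876.

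Each participant is 1/20 = 5% of an arm. If one differs by 1 point from the mean of the others, including or excluding that score moves the arm mean by 1/20 = 0.05; two such participants move it by 2/20 = 0.10. The standard error of a 20-person arm mean at SD 1.0 is 1/√20 = 0.22. Both the count (0 to 2 per arm) and the 1-point difference are assumptions.

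**The case against.** The gap may not exist. The reference to Day 42 can be read as extending the window to that day, and the neighbouring post-baseline windows adjoin (Days 16/17, 42/43, 70/71), which suggests that a table without gaps was intended. This stands as an ambiguity. On that reading, however, the 3-day wording does no work, so a cap is the more natural sense. SAP 9 requires two independently programmed datasets to match fully, so one meaning has to be fixed either way.

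A reader might infer that anyone whose dosing was interrupted or stopped early is lost. The documents do not support that. The clinic dose covers those who resumed, and Protocol 7.1 with SAP 6.2.3 covers those who exit. One limit remains on the second route: Protocol 7.2 calls for Exit visit procedures, and the Day 84 column of the schedule has no ocular photography, so there may be no photograph to map.

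The exposed group is also narrow. On-treatment chemistry is scheduled only at Day 28 and at an optional in-clinic Day 7. A liver-triggered hold still active at Day 28 therefore needs that optional visit or an unscheduled test. Holds for other safety signals remain possible. The Protocol 6.4 group is followed for safety, and no photograph is stated, so it counts only if one is taken.

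Finally, Visit 3 is labelled the end-of-treatment visit and is photographed after a dose, so a short post-dose limit can be defended as an on-drug definition. But the per-protocol set already answers that question, and SAP 5.3 gives no sign that mITT was meant to.

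**Conclusion.** The point holds for a scheduled Day 28 photograph from a participant still on hold at that visit, or taken off drug but kept in visits and photographed, with the last dose more than 3 days earlier. It rests on the cap reading. SAP 6 gives such a record no visit and so no primary change score, and this conflicts with the mITT wording in SAP 5.3.

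Two stronger conclusions are tempting. One is that these participants certainly leave the primary population. The documents do not say so: mITT is worded by visit, and which provision prevails is unresolved. The other is that mITT becomes close to an on-treatment set and favours the active arms. Neither the number affected nor the direction of bias can be derived from the documents, and 0 to 2 of 20 would not make it so.

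Under the stated assumptions the effect on an arm mean is 0 to 0.10, against a planned difference of 1. It is small, but it touches the primary endpoint and is easily removed.

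**What to change.** In the SAP 6 window table, define Visit 3 for efficacy as Day 17 to Day 42 regardless of the date of last dose, and use the record closest to Day 28. In SAP 5.3, state that dosing status at Day 28 affects neither mITT membership nor use of the observed score. No separate 3-day rule is needed for the per-protocol set, because its 4-of-6-doses rule already does that work.

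The cost is one table cell and one sentence, to be settled before the first database lock described in SAP 8, since the primary analysis is run then. No visit, procedure or treatment rule changes. The downside is slight dilution of the estimated effect if off-drug participants are retained; the per-protocol analysis still shows the on-treatment result.

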6.1 Participant Disposition

The number and percentage of participants will be summarized by the assigned treatment group and overall for the following:

- Participants screened, randomized, discontinued, completed treatment, completed study
- Participants in the safety population
- Participants in the mITT population
- Participants in the PP population
- Participants in the PK sub-study, if applicable
- Time in treatment, in study
- Participants at each visit
- Participants at each investigational site
- Participants discontinued and reason(s)
- Participants excluded from efficacy analysis and reason(s)

Individual participant disposition data will be listed.

6.2 Treatments

6.2.1 Extent of Study Drug Exposure

Exposure to treatment and treatment compliance will be summarized by the assigned treatment group.

Exposure (i.e., treatment time, days) will be determined as following:

$$\text{Time in Study Treatment (Treatment duration)} = \text{Date of Last Dose} - \text{Date of First Dose} + 1$$

Treatment compliance will be determined as study eye drops being used at least 70% of the time since last visit according to patient diary entries, AND at least 4 of the 6 scheduled applications in the 2 days prior to the visit.

Exploratory analyses will be conducted to understand the relationship between exposure and response.

6.2.2 Concomitant Medications

Concomitant medications taken during the study will be coded per the World Health Organization (WHO) Drug dictionary (WHODrug Sept 2017 version at the time of SAP publication, or the current version when superseded). When two medications are coded to the same preferred term, both will be counted.

Medications with partial dates that do not allow determination of whether prior or concomitant will be considered concomitant.

Participant listing of prior and concomitant medication will be presented.

6.2.3 Treatment Discontinuation and Rescue Medications

As there is no pharmacologic treatment for pterygium, no rescue medication is proposed in this study. Therefore, no switch treatment will be considered. The participant will be exited from the study after discontinuation from the study treatment. Investigators may direct participants to the use of eye drops (e.g., artificial tears, decongestant drops, etc.) as appropriate, to alleviate any symptoms related to the participant's condition.

Efficacy assessment collected from the treatment discontinuation exit will be mapped to the next scheduled visit and considered as observed data. (i.e., the mapping will be performed prior to any data imputation if any).

Safety assessment for the treatment discontinuation exit will not be mapped. Instead, it will be treated as the last assessment during treatment period.

6.3 Demographic and Baseline/Screening Characteristics

All demographic and baseline data will be summarized per the assigned treatment and overall using the safety population. The following variables will be presented:

- Age (years)
- Age group (18 - 35, 36 - 50, 51 – 65, ≥ 66 yrs)
- Gender (Female, Male)
- Child Bearing Potentials (for females only – No, Yes. If No, Reason - Bilateral oophorectomy; Bilateral tubal ligation; Hysterectomy; Post-menopausal)
- Ethnicity (Hispanic or Latino, Not Hispanic or Latino)

- Race (American Indian or Alaska Native; Asian; Australian Aboriginal or Torres Strait Islander; Black; Native Hawaiian or Other Pacific Islander; White. If Other, list of specified.)
- Iris Color (Black; Blue; Brown; Green; Grey; Hazel; Other. If Other, list of specified.)

6.4 Protocol Deviations

Individuals participant listing of protocol deviation will be provided.

6.5 Efficacy Evaluation

All efficacy analyses will be based on the mITT population.

The primary statistical approach for assessment of difference among the treatment groups in change from baseline to Day 28 in conjunctival hyperemia score will be based on a mixed effect model. Significant baseline characteristics and their interaction might be included as covariant. Mean changes for each treatment group and the differences in mean changes will be estimated with the Least-Square means generated by the mixed model. Multiplicity adjustment will be conducted with Bonferroni approach.

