### 9.4 STATISTICAL ANALYSES

#### 9.4.1 GENERAL APPROACH

The database will be locked after all participants exit the study and all data clarification forms or queries have been resolved. Prior to database lock, a detailed Statistical Analysis Plan (SAP) will be finalized and approved. Final analysis and unmasking of participants' treatment code will occur after database lock.

Wherever appropriate, summary statistics will include the sample size, mean, standard deviation (SD), median, minimum, and maximum for continuous and ordinal variables, and frequency counts and percent for categorical variables. Data will be presented by treatment (0.1% AG-86893, 0.3% AG-86893, AG-86893 vehicle). Additional analyses between vehicle and active drug will be explored, the details of which will be described in the SAP. All testing will be two-sided and will be performed without adjustment for testing multiple measures.

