3.4 Randomization and Masking

Eligible participants will be assigned in 1:1:1 ratio into 1 of the 3 treatment groups. A central randomization scheme will be prepared by an unmasked Trial Runners representative and dispensed via an Interactive Web Response System (IWRS). Randomization schedule will be optimized as much as possible to achieve a balanced distribution of treatment assignment by investigational site, baseline hyperemia severity (grade of 2 vs. > 2), and PK participation.

Randomization assignment will occur by site personnel via IWRS once a participant's eligibility is determined by the investigator and confirmed by the central reading center. The IWRS will provide a unique Subject ID to be used in all study documents as the study identifier.

Study drug will be labeled with medication kit numbers, and the IWRS will provide each site with the specific medication kit number(s) for each randomized participant at the time of randomization. Sites will dispense study drug according to the IWRS instructions. Sites will receive the IWRS confirmation notifications for each transaction. All notifications are to be maintained with the study source documents.

Treatment assignment will be masked to the study participants, the investigators, all study-site personnel (with the exception of the unmasked drug administrator), study monitoring personnel, as well as Central Reading Center personnel during the entirety of the study. Day 28 efficacy and safety results based on the 1st database lock will be presented with unmasked treatment group, but no disclosure of treatment assignment at individual participant level.

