6.5.2 Secondary and Exploratory Variables and Sub-Study Variables

Secondary, exploratory and exploratory sub-study numerical endpoints will be explored using the same approach as outlined for the primary efficacy analysis and might include the following:

- Change from baseline in conjunctival hyperemia score at the study quadrant at Days 28
- Change from baseline in pterygium vascularity at Days 28 and 56

- Change from baseline in pterygium vessel length at Days 28 and 56
- Change from baseline in Pterygium volume at Days 28 and 56
- IOP
- BCVA in letters read correctly
- Biomicroscopy parameters for conjunctiva, cornea, and iris. Lens status scale
- TFBUT
- Lissamine green conjunctival staining score
- Fundus
- Participant questionnaire

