APPENDIX 2 SAMPLE SAS CODE FRAGMENT

For estimation of main treatment effect:

SAS pseudo code for main treatment effect and LS mean estimation:

```
proc mixed data=xxx;  
  where mitt='Y'; *select the designated analysis population here (e.g.,  
  itt, pp);  
  class TREAT; *include other categorical covariants;  
  model CHANGE_OVERALL = TREAT/ddfm=statterth; *if any, include covariants  
  and interaction terms;  
  lsmeans TREAT/pdiff cl adjdfe=row adjust=bon;  
  (ods output statements)  
run;
```

SAS pseudo code for estimation of proportions and 95% CI, and the difference in proportions:

```
proc freq data=xxx;  
  tables VAR1 * VAR2/ alpha = 0.05 riskdiff (CL = MN);  
  * Miettinen and Nurminen inverted score test;  
  (ods statements)  
run;
```

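### The primary model could fix the Day 1 hyperemia score as a covariate, instead of leaving adjustment to an optional and undefined rule

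*SAP*

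**What the plan says.** SAP 6.5 bases the primary analysis of change from baseline to Day 28 on a mixed model and adds: "Significant baseline characteristics and their interaction might be included as covariant". It does not list the candidate characteristics, define significance for this purpose, say which interaction is meant, or say when the choice is made.

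The code in SAP Appendix 2 has treatment as its only term, with anything else conditional: "model CHANGE_OVERALL = TREAT/ddfm=statterth; *if any, include covariants". Protocol 9.3 is also dose-only: "analysis of variance models with dose strength as main effects". Protocol 9.4.2 adds no covariate.

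The Day 1 score is always available, because mITT membership requires that the participant "had conjunctival hyperemia evaluated at both the Day 1 and Day 28 visits" (SAP 5.3). Baseline severity already matters at allocation (SAP 3.4): "Randomization schedule will be optimized as much as possible to achieve a balanced distribution of treatment assignment by investigational site, baseline hyperemia severity". Under SAP 6.5.2 the secondary and exploratory endpoints "will be explored using the same approach as outlined for the primary efficacy analysis", so the open rule carries over to them. SAP 6.5.3 reuses the model for the per-protocol analysis.

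Protocol 9.4.1 says: "Prior to database lock, a detailed Statistical Analysis Plan (SAP) will be finalized and approved". That does not settle the choice, because the open sentence is in the SAP itself. SAP Module II (tables, figures and listings) was not available and could not be checked.

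**The concern.** Two things are at stake.

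- **Precision.** A change score without the baseline score as covariate implicitly sets the slope of Day 28 on Day 1 to 1. Where the true slope differs from 1, adjusting for the Day 1 score gives a smaller residual variance for one degree of freedom, using data already collected.
- **Prespecification.** SAP 6.5.1 controls the familywise error with a global test at 0.05 followed by Bonferroni pairwise comparisons, one of them for dose selection. That control presumes a single model, and SAP 6.5 allows more than one. The plan requires per-protocol exclusion rules to be made before lock (SAP 5.4) but sets no such limit for covariates. SAP 3.4 has Day 28 results presented by unmasked treatment group from the first database lock, so that is the natural deadline.

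**Working it through.** **Inputs from the documents.** 20 per arm, a difference of 1, and an SD of 1.0 stated for the mean overall score (protocol 9.2). Two-sided testing (protocol 9.4.1). Global test at 0.05, then three Bonferroni comparisons, each at 0.05/3 = 0.0167 (SAP 6.5.1).

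**Assumed, because the documents do not give them.** r = correlation of Day 1 and Day 28 scores (0.3, 0.5, 0.7); k = Day 1 SD / Day 28 SD (0.5, 0.7).

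**1. The plan's own figure.** One-way F test, group means 0, 1, 1, SD 1: noncentrality 20 × (4/9 + 1/9 + 1/9) = 13.33 on 2 and 57 df. Power is 0.8997, which matches the stated 90%. No covariate is involved. The Bonferroni pairwise test under the same inputs (noncentral t, 57 df) has power 0.754.

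**2. Effect of the covariate.** Taking the Day 28 SD as the unit:

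- variance of change = 1 + k² − 2rk
- residual variance given the Day 1 score = 1 − r²
- variance ratio, adjusted to unadjusted = (1 − r²)/(1 + k² − 2rk), with 56 error df

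The ratio equals 1 when r = k (slope r/k = 1), and there adjustment gains nothing. Example: k = 0.7, r = 0.3 gives 0.91/1.07 = 0.850.

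**3. Pairwise power, unadjusted → Day 1 score fixed.** The SD of 1.0 can be read in two ways, so both are shown.

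| k | r | Variance ratio | 1.0 = SD of change | 1.0 = SD of Day 28 score |
|---|---|---|---|---|
| 0.5 | 0.3 | 0.958 | 75% → 77% | 78% → 80% |
| 0.5 | 0.5 | 1.000 | 75% → 75% | 88% → 88% |
| 0.5 | 0.7 | 0.927 | 75% → 79% | 96% → 97% |
| 0.7 | 0.3 | 0.850 | 75% → 83% | 72% → 80% |
| 0.7 | 0.5 | 0.949 | 75% → 78% | 86% → 88% |
| 0.7 | 0.7 | 1.000 | 75% → 75% | 97% → 97% |

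**4. Which cells are plausible.** If 1.0 is the SD of change, the Day 1 SD is k/√(1 + k² − 2rk): 0.51/0.58/0.67 at k = 0.5 and 0.68/0.79/0.98 at k = 0.7. For comparison, the 336 grade patterns that meet protocol 5.1, weighted equally for illustration, have SD 0.58. Restricting them to an overall score of at least 2 (protocol 4.1) gives 0.45. The largest gain needs a Day 1 SD of about 0.68 to 0.70, above both. The cell k = 0.5, r = 0.7 implies a slope of 0.7/0.5 = 1.4 (redder eyes diverging further), which is a strained case.

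**5. Cost where there is no gain.** By formula, 75.44% falls to 75.40%. Simulation (40,000 trials per cell, SD of change 1.0), which also counts chance baseline imbalance, gives 75.3% to 74.5% and 75.2% to 74.3%.

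**6. Null rejection of the global test, nominal 5%, k = 0.5 to 0.7, same simulation size.**

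| Rule | Rejection |
|---|---|
| Day 1 score fixed | 4.8–5.3% |
| Day 1 score kept if p < 0.05 | 4.9–5.6% |
| Better of unadjusted and adjusted | 5.3–7.0% |

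**The case against.** The strongest reply is that nothing here is wrong. The trial is exploratory, a change-score comparison is unbiased under randomization, allocation is balanced on baseline severity as far as possible, and the power claim reproduces without a covariate. The gain is zero in two of six cells and small in the cells nearest the eligibility benchmarks. A mechanical p < 0.05 screen of the Day 1 score would do about as well: simulated power is 81.9% against 82.1% with the score fixed at k = 0.7, r = 0.3, and 75.4% against 74.5% at k = r = 0.5. All of this stands. It limits the size of the point but does not close the model, because SAP 6.5 states no screen, mechanical or otherwise.

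Three stronger readings are tempting, and the documents do not support them.

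- **That the plan inflates the type I error.** The inflation in step 6 needs someone to take the more favourable result. The plan does not propose this; it only fails to exclude it.
- **That adjustment would raise pairwise power to around 90%.** With equal Day 1 and Day 28 SDs (k = 1) and 1.0 as the SD of change, the formula gives 88% at r = 0.5 and 92% at r = 0.3. Those need a Day 1 SD of 1.00 and 0.85, which the eligibility thresholds may not allow.
- **That the SAP excludes the Day 1 score as a candidate because section 6.3 omits it.** That section introduces a summary list: "All demographic and baseline data will be summarized per the assigned treatment and overall using the safety population. The following variables will be presented". It is not a covariate list. SAP 6 defines baseline results as those recorded before dosing, and SAP 3.4 names baseline hyperemia severity, so the score may well be a candidate. The documents do not say.

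**Conclusion.** The point holds as an improvement in efficiency and prespecification, not as an error in the analysis. The text is clear: treatment is the only fixed term, adjustment is optional and undefined, and the obvious covariate is available for everyone analysed but not named.

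The precision gain is less certain: 0 to about 8 points of pairwise power over the assumed r and k, with a loss of at most about 1 point. That range depends on r and k, which are assumptions, and the starting level depends on whether 1.0 is the SD of the change or of the Day 28 score. Protocol 9.2 states it for the score. The case for settling the model before treatment-group results are seen does not depend on any gain in power.

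**What to change.** - **SAP 6.5 and Appendix 2:** set the primary model as change = treatment + Day 1 overall hyperemia score, continuous.
- **SAP 6.5.2:** for the pterygium-quadrant endpoint, use that quadrant's own Day 1 score.
- **Other covariates and interactions:** remove the open sentence, or confine it to analyses labelled supportive, with candidates and threshold fixed before the first database lock.
- **Unadjusted model:** keep it as a supportive analysis.
- **Protocol 9.3:** it specifies a dose-only analysis of variance, so either align it or record the departure in SAP 1.1.

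The cost is wording in the SAP (and in the protocol if it is aligned), one line of code and one degree of freedom. No new data or participants are needed.
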